Title of Study: ATTAC-MCC: Phase I/II study of Autologous CD8+ and CD4+ Transgenic T cells expressing high affinity MCPyV-specific TCRs combined with Avelumab and Class I MHC - upregulation in patients with metastatic MCC refractory to PD-1 axis blockade		
Sponsor: Fred Hutch		Phase of Development: I/II
Study Objectives: Primary: Safety, Efficacy Secondary/Exploratory: T cell persistence, T cell phenotype, T cell function, T cell localization into tumor, epitope spreading of T cell responses, recurrence-free survival, overall survival		
Study Purpose and Rationale: 
Metastatic Merkel cell carcinoma is an aggressive skin cancer caused by a virus. There are currently no effective treatments for individuals whose cancer progresses on or after treatment with PD-1 axis immunotherapies. We have developed an engineered autologous T cell therapy targeting Merkel cell polyomavirus. In a phase I/II trial, we seek to determine the safety and potential efficacy of this T cell therapy combined with interferon gamma, in addition to standard treatments (anti-PDL1/avelumab) for patients whose virus-associated metastatic/unresectable MCC tumors are resistant to PD-1 axis treatments.
		
Study Population: 
Individuals that are HLA-A02+ with metastatic Merkel cell polyomavirus associated Merkel cell carcinoma whose disease has progressed on or after treatment with a PD-1 axis checkpoint inhibitor
		
Test Product: 
 - FH-MCVA2TCR: Autologous CD8+ and CD4+ T cells transduced with transgenic TCR A2-MCC1. - Interferon gamma 		
Additional Interventions (not test product, given as standard of care): 
 - Avelumab - Pembrolizumab (as an alternative to avelumab) 		
Safety Assessments: Ongoing; with evaluation of part I/II transition after three patients have been treated		
DLT Definition: 
DLTs will be assessed for 28 days following the infusion of the TCR transgenic T cell product. The following events will be considered DLTs if they are attributed as at least possibly related to TCR T
		

cell administration. Grading will be done in accordance with NCI CTCAE version 5.0 unless otherwise specified.

1. Grade 3 allergic reaction or other event that leads to discontinuation of TCR T cell infusion
2. Grade 3 autoimmune reactions
3. Grade 3 neurotoxicity that does not resolve to grade 1 or less within 7 days
4. Grade 3 CRS that does not resolve to < grade 3 within 7 days.
5. Grade 4 organ toxicity not pre-existing or due to the underlying malignancy and occurring within 28 days of study product infusion.
6. Any other toxicity not meeting above criteria that is deemed by the PI to represent a DLT.

Efficacy Assessments: At completion of study

Statistical Methods: Phase I/II interventional trial, not masked, dose-escalation. Goal grade 3+ treatment related toxicity rate of <40%; likelihood of stoppage if true rate 25% is 0.05. Response determination by RECIST 1.1 with goal response rate statistically >5%; power to detect this is true response rate is 20% is 0.84. All secondary and exploratory endpoints exploratory.

Sample size: up to 16 participants

TABLE OF CONTENTS

Protocol Synopsis	3
1. BACKGROUND.....	9
2. STUDY PURPOSE AND RATIONALE.....	10
2.1 Rationale for Investigation of FH-MCVA2TCR	10
2.1.1 Scientific basis for T cell therapy targeting MCPyV in MCC.....	10
2.1.2 Target epitope: "KLLEIAPNC" MCPyV Epitope	11
2.1.3 Clinical experience with T cells targeting MCPyV in MCC:.....	11
2.1.4 Rationale for Transgenic T cell approach	13
2.1.5 Transgenic TCR vs. Transgenic CAR.....	14
2.1.6 Safety of TCR transgenic T cells for other cancers.....	14
2.1.7 TCR A2-MCC1 is a highly potent natural TCR that effectively lyses MCC cell lines	14
2.1.8 Evaluation of potential for off-target activity and cross or allo-reactivity of TCR A2-MCC1	15
2.1.9 Rationale for using a third-generation lentiviral vector.....	15
2.1.10 Rationale for substrate T cell of CD62L+ ("young" but well differentiated) CD8+ T Cells.....	17
2.1.11 Rationale for inclusion of transgenic CD4+ T cells in addition to transgenic CD8+ T cells	17
2.1.12 FH-MCVA2TCR Dose Rationale	18
2.1.13 Rationale for omission of Lymphodepleting Chemotherapy prior to T cell infusion.....	18
2.2 Rationale for inclusion of subcutaneous interferon gamma	19
2.2.1 Scientific basis.....	19
2.2.2 Interferon Gamma- Preclinical results	19
2.3 Rationale for administration of TCR-transgenic T cells in the context of treatment with avelumab or Pembrolizumab as a standard of care	21
2.3.1 Avelumab and Pembrolizumab - Scientific basis	21
2.3.2 Avelumab - Clinical experience & safety.....	21
2.4 Rationale for inclusion of biopsies	22
3. STUDY OBJECTIVES	22
3.1 Primary Objectives	22
3.1.1 Safety.....	22
3.1.2 Efficacy.....	23
3.2 Secondary Objectives	23

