4.4 Staggering and Dose Escalation

At least three patients will be treated on part I. In part I, patients will be treated with a lower-dose first infusion. Each part I patient must complete their dose-limiting-toxicity (DLT) evaluation period (28 days) after their first T cell infusion before the next part I patient may receive their first infusion. This allows for an ample buffer/window to evaluate for potential cytokine release syndrome and/or neurotoxicity, before proceeding to next patient. After three patients have received their first T cell infusion and completed the 28 day DLT evaluation after the lower first dose infusion, with one or fewer patients experiencing grade 3-4 d related adverse events as defined in **Section 12**, the study may move to part II. If two or more of the first three patients have a treatment-related grade 3 or 4 toxicity, or if any of the first three patients experiences a treatment-related death, at that point the trial will be immediately suspended. We will consult with the data and safety monitoring board (DSMB), and a detailed review of the potential causes of toxicity undertaken. We will reconvene with the DSMB and consideration will be given to changing the cell dose or construct if the T cells were implicated. In that scenario, the dose escalation will be restarted and an additional three patients treated before proceeding to the part II portion of the study. Part I will continue until 3 patients are treated at the lower dose level. If the manufacturing process is short of the intended dose targeted for the patient, whatever smaller dose is available from a single manufacturing run will be given.

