For the first three patients treated on part II, the staggering interval will continue as for part I, with each treated patient completing their 28-day DLT evaluation period after first T cell infusion before the next part II patient may be treated at that dose. If two or more of the first three part II patients have a treatment-related grade 3 or 4 toxicity, unless a toxicity specifically accepted in **Section 12.5 and 12.6**, or if any of the first three patients experiences a treatment-related death, at that point the trial will be immediately suspended. We will consult with the data and safety monitoring board (DSMB), and a detailed review of the potential causes of toxicity undertaken. We will reconvene with the DSMB and consideration will be given to changing the cell dose to the part I dose level and/or other protocol modifications on guidance of the DSMB. If instead three part II patients have received their first T cell infusion and completed the 28 day DLT evaluation after the lower first dose infusion, with one or fewer patients experiencing grade 3-4 related adverse events as defined in **Section 12**, staggering restrictions will be lifted and there will be no specific staggering requirement.

As patients eligible for second infusion will have tolerated a previous exposure to the same T cell product, between-patient staggering intervals will not apply for second infusion. However, patients will be monitored for a second 28-day DLT period and safety events recorded. Patients previously treated with lower doses of T cells on earlier versions of this trial will be eligible to receive up to an additional 2 doses of TCR transgenic T cells, starting at the dose level for newly entering patients provided that they meet eligibility criteria in **Section 5** before each additional dose.

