13.2.2 Definition of success and probability of suspension

Platinum-based combination chemotherapy is associated with 30 to 40% grade ≥ 3 toxicities⁴⁶ and although data are not yet available for MCC, combination checkpoint inhibitors see 45-55% treatment associated grade ≥ 3 toxicity in patients with metastatic melanoma.⁶⁹ To avoid exceeding these toxicity

rates, the treatment will be considered to have an acceptable safety profile if the observed toxicity rate is consistent with a true rate that does not exceed 40%.

Evidence of excessive toxicity will be an observed proportion of toxicities for which the associated lower 80% confidence limit exceeds 40%. Operationally, this limit will be met if any of the following proportions is observed: 2/2, 3/3-4, 4/5-6, 5/7-8, 6/9-10, 7/11-12, 8/13-14, 9/15-16. Under these rules, if the true probability of toxicity is 20%, the probability of suspension is approximately 0.06. If the true probability of toxicity is 60%, the probability of suspension is approximately 0.84 (based on 5,000 simulations).

The initial three part I patients will be treated and followed for toxicity. All three of these patients will receive their first cycle of treatment (T cell infusions) before additional patients will be enrolled. If zero or one of the first three part I patients experiences treatment-related and grade ≥ 3 toxicity, the remaining (up to) 13 pts will be treated on the part II portion of the trial. If instead two or more of the first three patients experience grade 3 toxicity, at the point that the two toxicities occur, the trial will be suspended and, after a detailed review of the potential causes of toxicity, consideration given to changing the cell dose or construct pending DSMB review. If any of the first three patients experience treatment related death, the trial will be suspended and, after a detailed review of the potential causes of toxicity, consideration given to changing the cell dose or construct pending DSMB review. As detailed in **Section 11.7**, if at any point any patient experiences grade 3 or higher treatment-related toxicity, that particular patient will no longer receive study related active therapies, except as specified in **Section 12.6.1**. They will continue to be followed for response and outcome.

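### The synopsis gives a 0.05 chance of stopping at 25% toxicity, but the Section 13.2.2 boundaries give 0.11; the 0.06 and 0.84 in 13.2.2 cover only the listed proportions and should say so

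*Combined protocol and SAP*

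**What the plan says.** The synopsis (Statistical Methods) sets a goal of a grade 3 or higher treatment-related toxicity rate below 40% and gives one operating characteristic: "likelihood of stoppage if true rate 25% is 0.05".

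Section 13.2.2 defines excessive toxicity as a lower 80% confidence limit above 40% and lists the proportions that meet it: "2/2, 3/3-4, 4/5-6, 5/7-8, 6/9-10, 7/11-12, 8/13-14, 9/15-16". It continues: "Under these rules, if the true probability of toxicity is 20%, the probability of suspension is approximately 0.06", and "If the true probability of toxicity is 60%, the probability of suspension is approximately 0.84 (based on 5,000 simulations" in number). It gives no figure for 25%.

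Other suspension rules stand beside the list:

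- **Part I, in 13.2.2 and again in 4.4.** The next paragraph of 13.2.2 has "If instead two or more of the first three patients experience grade 3 toxicity", and 4.4 has "If two or more of the first three patients have a treatment-related grade 3 or 4 toxicity".
- **Part II, in 4.4 only.** "If two or more of the first three part II patients have a treatment-related grade 3 or 4 toxicity", the trial is likewise suspended.
- **Deaths.** 13.2.2 has "If any of the first three patients experience treatment related death, the trial will be suspended". Section 4.4 has a death rule for the first three patients of each part.

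Section 14.2 asks the DSMB to judge excessive toxicity consistently with Section 13.

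**The concern.** Two things looked wrong. First, the synopsis reports a smaller chance of stopping at 25% than 13.2.2 reports at 20%. For a fixed set of boundaries that is impossible, so at least one figure is wrong or rests on an unstated basis.

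Second, 13.2.2 speaks of the probability of suspension without saying that its figures cover only the listed proportions. At three patients the list requires 3/3, yet the next paragraph suspends at two of three. The part II triggers do not appear in Section 13 at all, although that is the section the DSMB is pointed to. A reader of Section 13 alone would take 0.06 as the chance that a treatment with a 20% toxicity rate is suspended, and would not see that 4.4 can suspend the trial when the list does not.

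Safety is a primary endpoint and these are its only stated operating characteristics.

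**Working it through.** **Inputs.** Maximum of 16 patients (13.1). Listed boundaries from 13.2.2: 2 toxicities at n = 2; 3 at n = 3–4; 4 at 5–6; 5 at 7–8; 6 at 9–10; 7 at 11–12; 8 at 13–14; 9 at 15–16. Two-of-three rules from 4.4 and 13.2.2.

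**Check of the boundaries.** For each n from 2 to 16, the smallest count whose one-sided 80% Clopper-Pearson lower limit exceeds 0.40 equals the listed count. The list is what the text says it is.

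**Method.** An exact recursion over patients 1 to 16: carry the probability of each toxicity count, and remove it the first time the count reaches the boundary. With true rate p, the first two terms are

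- n = 2: p²
- n = 4: 2p³(1 − p), that is, one toxicity in the first two patients and then two more.

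**The plan's own figures (list only).** At 20% the exact value is 0.0623 (stated 0.06). At 60% it is 0.8473 (stated 0.84). Both reproduce.

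**The synopsis figure (list only, p = 0.25).** Probability of first crossing at each n:

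| n | 2 | 4 | 6 | 8 | 10 | 12 | 14 | 16 |
|---|---|---|---|---|---|---|---|---|
| Probability | 0.0625 | 0.0234 | 0.0110 | 0.0058 | 0.0032 | 0.0019 | 0.0012 | 0.0007 |

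The sum is 0.1097. The first term, 0.25² = 0.0625, already exceeds 0.05. The 95% simulation error with 5,000 runs is 1.96 × √(0.11 × 0.89 / 5,000) ≈ 0.009, too small to explain the gap. The list reaches 0.05 at a true rate of 18.3%.

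**Could another reading give 0.05 at 25%?**

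- Monitoring only from patient 5 gives 0.0548, but it drops listed looks and gives 0.023 at 20%, against the stated 0.06.
- A part I rate of 15.3% with part II at 25% gives 0.050, but the same ratio of rates gives 0.026 when part II is 20%.
- Adding the two-of-three rules moves the figure further from 0.05 (next table).

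**Adding the two-of-three rules.** Assumptions: patients 1–3 are part I and patients 4–6 are the first three of part II; rates are equal and independent; every rule counts the same events; no deaths; no restart.

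| True rate | List only | List + part I rule | List + both rules |
|---|---|---|---|
| 20% | 0.062 | 0.110 | 0.198 |
| 25% | 0.110 | 0.1725 | 0.290 |
| 60% | 0.847 | 0.871 | 0.920 |

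**Sensitivity of the combined figure (list + both rules).**

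| Part I / part II rate | Share of events counted by the two-of-three rules | List only | Combined |
|---|---|---|---|
| 10% / 20% | all | 0.019 | 0.129 |
| 10% / 20% | half | 0.019 | 0.048 |
| 5% / 20% | a quarter | 0.007 | 0.014 |
| 40% / 60% | all | 0.720 | 0.845 |
| 40% / 60% | half | 0.720 | 0.754 |

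If 5% of toxicities were fatal and the death rules applied, the 20% / 20% figure with all events counted would rise from 0.198 to 0.232.

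**Where the list and 4.4 part company at a 20% rate.** P(2 or more of 3) = 3 × 0.2² × 0.8 + 0.2³ = 0.104.

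- None of three in part I, then at least two of three in part II: 0.8³ × 0.104 = 0.512 × 0.104 = 0.053. The running count is 2/6 or 3/6, below the list's 4/6.
- One of three, then exactly two of three: 0.384 × 0.096 = 0.037. The count is 3/6, again below 4/6.

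In both cases 4.4 suspends while the list has not been met. Together: 0.053 + 0.037 = 0.090.

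**The case against.** The best defence is that 13.2.2 is the operative text and its figures are right. In that section, the words introducing the 0.06 follow directly on the list, and the two-of-three rule comes in a separate paragraph, so applying the figures to the list is a fair reading. No rule is missing from the protocol: 4.4 suspends the trial whatever Section 13 repeats, and the DSMB also works to a charter that is not among the documents. The 4.4 rules are early gates, written in terms of grade 3–4 events and a 28-day window, whereas 13.2.1 counts any grade 3 or higher event related to any study treatment. The first infusion in part I is at a five-fold lower dose. Combined figures that assume equal rates and identical events therefore go beyond what the documents supply.

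Most of this stands. It limits the second point to labelling and cross-reference, and it makes the combined figures illustrations rather than corrections. The comparator for the synopsis is 0.110, not 0.1725 or 0.290.

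It does not rescue the synopsis. The 0.05 may be a transcription slip: the synopsis pairs safety with 25% and efficacy power of 0.84 with 20%, while Section 13 pairs safety with 20% and 84% power with 25%. A swap of the two rates is plausible, but it would leave 0.05 against 0.06. It is a reason to check both synopsis sentences together.

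**Conclusion.** The concern holds. The synopsis figure of 0.05 at 25% is wrong: the listed boundaries give 0.110, and no reading tried gives 0.05 at 25% while keeping 0.06 at 20%. This rests only on the list, 16 patients, and independent outcomes with a common rate.

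The 0.06 and 0.84 in 13.2.2 are correct for the listed proportions but are not the trial's overall probability of suspension. The added rules can only raise it. By how much depends on the rate in each part, which events each rule counts, and deaths; with part II at 20%, the cases examined run from 0.014 to 0.232.

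The consequence is moderate. The rules in 4.4 make the trial more protective than the stated figures suggest, and the efficacy test is unaffected. This should be fixed because it misstates an operating characteristic of a primary endpoint and leaves Section 13 incomplete for the DSMB.

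**What to change.** 1. Correct the synopsis to agree with 13.2.2 and name the rules covered: for the listed proportions, 0.06 at 20% or 0.11 at 25%. Check the synopsis efficacy sentence against 13.3.2 at the same time.
2. In 13.2.2, label 0.06 and 0.84 as covering the listed proportions only, separately from the part I two-of-three rule in the next paragraph.
3. Reconcile Section 13 with 4.4 by carrying over or cross-referencing the part II two-of-three and death rules, and state that, as the passages now read, any one trigger suspends the trial.
4. Report the combined probability of suspension with its assumptions: rate in each part, events and time window counted by each rule, deaths, and whether a restart is included. The equal-rate values above can serve as one labelled illustration.

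The cost is a short re-run and wording changes in the synopsis and Section 13. No trigger, sample size or test changes, and none is proposed here. The one drawback is that the reported chance of suspending an acceptably safe treatment becomes less favourable.

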1. BACKGROUND

This document is a clinical research protocol and the described study will be conducted in compliance with the IRB approved protocol

Merkel cell carcinoma (MCC) is a highly aggressive skin cancer, with an incidence that has doubled since the year 2000 to over 2500 cases/year in the US.¹ Over one-third of patients will develop widespread disease, and survival in these patients has been historically poor with a 5-year survival rate of <10%.² MCC is very immune sensitive, with better immune responses being associated with better disease outcomes.³ This is due to the strong antigenicity (visibility to the immune system) of the cancer-causing viral (Merkel cell polyomavirus; MCPyV) oncoproteins expressed in most MCC tumors.^{4,5} Hence, immune therapies, particularly those targeting the viral oncoproteins may be effective for MCC treatment. Indeed, recent international studies led out of Fred Hutchinson Cancer Center (Fred Hutch) have demonstrated that immune checkpoint inhibitors (ICIs) targeting the PD-1 axis (including pembrolizumab/Keytruda and avelumab/Bavencio) have efficacy, with one third to one half of the treated patients experiencing disease shrinkage and a small minority of patients (<10%) experiencing complete response.^{6,7} These demonstrate the potential for immunotherapy in MCC. However, for the majority of patients these treatments alone are ineffective and additional treatments are needed. We hypothesize that the patients who do not respond to checkpoint therapy alone have insufficient quantity of and/or poor-quality antiviral (and thus antitumor) T cells. Thus, we believe adding T cell therapies to the standard of care ICI avelumab⁷⁻¹² and administration of interferon gamma to facilitate T cell expansion (and increase the visibility of the tumor to the immune system) may be able to rescue patients who do not respond to an ICI alone.

In our previous Fred Hutch protocol 9245, we have combined avelumab, class I HLA upregulation, and autologous bulk expanded antiviral T cells in patients with advanced MCC.¹³ Seven patients have received T cells as of October, 2018, with no unexpected toxicities. Encouragingly, three patients had durable complete responses (CRs) and a fourth patient had a non-durable partial response (PR). ICI have only recently become available for treatment of MCC, and treated patients on 9245 represent a mix of those with and without prior immune checkpoint inhibitor (ICI exposure). However, due to availability, accessibility, safety and cost considerations for the current protocol 9845/ATTAC we will focus on patients in second-line (failure of ICI monotherapy) where the clinical need is greatest and where there are no available FDA-approved treatments.

Although previous protocols had success with bulk expanded/endogenous T cells, generation of these endogenous T cells is an expensive and slow process. In addition, it is difficult to achieve the required dose as patient-derived MCPyV-specific T cells are poorly avid and are rare or undetectable.⁵ Therefore, in the current proposed ATTAC regimen we are switching to a transgenic approach, which will allow us to deliver T cells to more patients, more cheaply, in greater numbers, and of higher quality (higher avidity). Similar transgenic T cells with a different target protein have been delivered to individuals with other malignancies including non-small cell lung cancer, mesothelioma, and acute myeloid leukemia.¹⁴

The present protocol, Protocol 9845: The ATTAC-MCC trial, is a phase I/II trial of the ATTAC regimen in patients with advanced MCC that has progressed on or after treatment with immune checkpoint (PD-1 or PD-L1 inhibitor) therapy. The ATTAC regimen is a combination of the FH-MCVA2TCR autologous transgenic CD8+ and CD4+ T cells carrying the transgenic TCR A2-MCC1 targeting the MCPyV,

avelumab or pembrolizumab (PD-L1 and PD-1 inhibitors approved by the FDA for treatment of Merkel Cell Carcinoma), and class I MHC upregulation in the tumor tissue with interferon gamma. In part I (until safety demonstrated in 3 consecutive participants), participants will receive a lower dose of T cells for first infusion (5-fold dose reduction from target dose). If adequate safety profile is observed, we will proceed to part II; if adverse safety signal is seen, we will re-design trial in consultation with our DSMB and restart part I. In part II, participants will receive full dose of T cells for both infusions. We anticipate enrolling up to 16 HLA-A02+ participants with Merkel cell polyomavirus positive advanced MCC over 2 years.

We hope that study participation will provide direct benefits to the treated patients. This study will also benefit the research field for immunotherapy development for MCC and cancer more generally. Merkel cell carcinoma is an ideal cancer in which to develop immunotherapies due to the target of the viral oncoprotein which is immunodominant. This allows us to give T cells that are more on-target (with less risk of immune related adverse events; iRAEs) and also to more closely monitor immune responses to the cancer. If treatment is successful, as we are hopeful based on our early success with similar approaches as above, similar regimens could be expanded to other malignancies. If treatment is unsuccessful, our sophisticated immunological monitoring of the infused cells, native immune cells, and tumor tissues will allow for a cutting edge, comprehensive understanding of the mechanisms for tumor immune evasion that will provide essential data for developing new and better immunotherapies for MCC.

